Protocol Cover Page

Title: Familial Hyperlipidemia Family Registry

NCT Number: 05814419

Version Date: 02MAR2023

Protocol: Familial Hyperlipidemia Family Registry

Principal Investigator(s): [name]

Main Study Site: [name]

Protocol Version Date: March 2, 2023

Protocol Version Number: 2

IRB # 22-1979

I. Hypothesis and Specific Aims

If a child from the Healthy Hearts and Minds education and screening program is found to have a genetic marker for familial hyperlipidemia, immediate family members are offered genetic testing at no charge to identify those at high risk for cardiovascular disorders and those who carry the genetic markers. If identified early, the risk for cardiovascular disease can be greatly modified by early and proper treatment.

The aim of the study is to gauge the impact of large-scale surveillance testing to identify those with the disorder and improve clinical care. This impact is both in disease prevention and in lessening the cost of long-term care from premature cardiovascular disease.

II. Background and Rationale

UCHealth Healthy Hearts and Minds education and screening program routinely screens 5th, 7th, and 10th graders for lipid and blood pressure status on an annual basis. Children with cholesterol levels greater than 200 mg/dl have been invited to participate in a Familial Hyperlipidemia protocol to identify individuals/families with genetic markers for lipid disorders.

Familial hyperlipidemia has four primary genetic types – LDL, LDLR, PCSK9 and Apo lipoprotein B. Individuals with familial hyperlipidemia, either heterozygote or homozygote, are at increased risk for cardiovascular events starting early in life.

Approximately 1 in 300-500 people have the heterozygote genetic profile, where as a homozygous genetic profile is very rare at 1 per one million. The cardiovascular risk for heterozygotes is increased 5–10 times over the normal population and the process begins much earlier in life. If these individuals are identified early, they have a greater than 80% chance to decrease their long-term risk of cardiovascular disease and have risks similar to the normal population.

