Recent evidence show that a small percentage of relatives pursue follow-up testing despite having a 50% risk of having the same variant. Reasons for not pursuing the testing include lack of knowledge about the potential disease risk, family communication barriers, lack of access to genetics services, and cost of testing.

Healthy Hearts and Minds partnered with Invitae to utilize their family variant testing. Invitae offers a no charge genetic test to biological family members for the variant that the biological related child tested positive for. Invitae provides no cost testing as a

commitment to lowering barriers to genetic testing and to increase access to genetic information that can help family members make informed health decisions.

III. Research Methods

a. Outcome measures: Children from the Healthy Hearts and Minds education and screening program who have been identified as having elevated cholesterol >200 mg/dl will be invited to be tested for genetic markers of Familial Hyperlipidemia. If positive for LDL, LDLR, PCSK9 or Apo lipoprotein B, immediate family members will be offered free lipid profiles, free genetic testing and referral to appropriate consultation for treatment of lipid disorders in adults or children. Family trees will be developed to ensure contacts are complete so each individual is allowed access to the lipid and genetic testing. The registry will catalogue family trees of the affected families to allow better identification of those who have the variant.

General health and medical information will be collected. A health questionnaire relating to cardiovascular disease and cardiovascular risk factors will be filled out for each biological family member (Appendix A). This will include questions about heart disease, high blood pressure, elevated cholesterol, and health habits. REDCap will be utilized to administer questionnaires. These forms will be collected, uploaded and stored in secure databases that only the research team will have access via their secure login and password. All data will be de-identified when presented outside of study.

b. Description of population to be enrolled:

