Inclusion criteria: Any biological relative of the child who had a positive result for familial hyperlipidemia that participated in the “School-based Education and Screening Program with Lipid Screening as a Means to Identify Familial Hyperlipidemia study” (IRB 20-6010) will be invited to enroll. Children from 6 months old to adults of any age may enroll.

As the genetic test will be provided by Invitae for no cost to all biological family members of the identified child as part of the family variant testing program, the number of genetic tests performed is not restricted by budgetary constraints. In addition, the limitation for numbers to enroll is based on the number of children from the familial hyperlipidemia study that are discovered to have a positive result for the gene and the number of biological relatives that request to receive a free genetic test. It is estimated that 10-20% (approximately 10-20 children) who enroll in the IRB 20-6010 study will be positive for familial hyperlipidemia and therefore no more than 5,000 biological relatives will enroll in this study.

Exclusion criteria: A participant may not enroll in the study if they are not biologically related to a child who was informed they have a positive result for familial hyperlipidemia from the IRB 20-6010 research study.

c. Study Design and Research Methods:

Children from the Healthy Hearts and Minds education and screening program identified as having elevated cholesterol >200 mg/dl will be tested for genetic markers of Familial Hyperlipidemia as part of the IRB 20-6010 study, which began in August 2022. Only the biological family members of a child with a positive test will be included in the study.

It is the responsibility of that child's parent or guardian to contact extended biological family members and inform them of their ability to receive their own family genetic testing kit. A flyer (Appendix B) will be provided which they can send to their immediate family members that will inform them on how to receive the free genetic test.

The family members have 150 days from the child's positive result to receive a free genetic test from Invitae. Once they contact the Healthy Hearts and Minds Research team, they will schedule their study visit to perform the genetic test and lipid panel. If the biological family member has already completed a genetic test or lipid panel, they can provide us with the testing results.

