- **Invitae genetic testing kit:** A buccal cheek swab will be utilized to collect the sample. The participant will be required to not have had any food or drink 30 minutes before the cheek swab. If the participant has previously performed the test for LDL, LDLR, PCSK9 and Apo lipoprotein B, they can opt out of the buccal swab and provide a copy of their familial hyperlipidemia results.
- **A lipid panel:** A finger stick utilizing the CardioChek Plus analyzer will be used to collect the sample. The test utilizes capillary blood and will provide results for HDL (high density lipoprotein), LDL (low density lipoprotein), and triglycerides. If the participant has already performed a lipid panel in the previous year, then they can opt out of the finger stick and provide a copy of their recent lipid panel results.

Results will be provided to the family when processed and available in approximately 4-12 weeks. The results will also be scanned and entered into the child's electronic medical records (EMR). A copy of the genetic test results can be forwarded to the child's primary care provider if requested. All participants will be offered access to clinical care for their lipid abnormalities, either through Cardiology or Pediatrics. Cost of care will be through their insurance carrier.

D. Description, Risks, and Justification of Procedures and Collection Tools.

There are no significant risks from this study. For the genetic test, there may be a slight discomfort with the cheek swab. Staff will utilize CardioChek devices and collect blood with a small finger stick blood sampling method. Risks for this capillary blood sampling are minimal, but include potential discomfort, bruising and infection.

Proper blood safety standards will be followed to minimize any potential participant and screener risk.

E. Potential Scientific Problems. There are no factors that could threaten our ability to obtain meaningful generalizable knowledge other than hesitation by a family to bring their child in to participate in a study during a pandemic may confound our sample.

F. Data Analysis Plan. Data from the family members will be tabulated and analyzed to create a family tree using R Studio and excel. Percent of family members tested who have familial hyperlipidemia will be calculated as well as estimated health care cost saving with early identification of families with the disorder.

G. Summarize Knowledge to be Gained:

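### Section F plans a cost saving from early identification, but Appendix A has no structured item that reliably separates newly identified carriers from those already diagnosed or treated

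*Combined protocol and SAP*

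**What the plan says.** Section F (Data Analysis Plan) names two numerical results: the percent of tested relatives who are positive, and an "estimated health care cost saving with early identification of families with the disorder". It does not say which positive relatives enter the saving.

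Section I explains where the benefit should come from: with early identification, "the risk for cardiovascular disease can be greatly modified by early and proper treatment". Sections I and G both make lower long-term care cost part of the aim.

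On who enrols, section III.b says "Children from 6 months old to adults of any age may enroll". The only exclusion is not being biologically related to a positive child. Prior diagnosis and current treatment are not mentioned.

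On data, section III.a describes a questionnaire (Appendix A): "This will include questions about heart disease, high blood pressure, elevated cholesterol, and health habits". Appendix A as printed lists name, relationship and side of family, age, gender, ethnicity, BMI, dated lipid values, one open line for CVD risk factors, one open line for CV disease, and other family members. Under Sample collection in III.c, a relative with an earlier gene test may skip the swab: "they can opt out of the buccal swab and provide a copy of their familial hyperlipidemia results". A relative with a lipid panel from the previous year may likewise supply that result.

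**The concern.** A saving from early identification belongs to people whose condition was found because of the program and who were not already being treated. An older relative on lipid-lowering treatment may carry the variant and test positive, but the treatment benefit was there before the test.

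The registry is likely to meet such people. It is open to adults of any age, and Appendix A's own examples of relatives include parents, a grandfather and an aunt. If their status is not recorded at the single visit described, the analyst cannot supply it later. The cost result, and any statement about how many carriers the program newly found, would then rest on a group that the data cannot define.

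**Working it through.** The documents give no cost figure to reproduce, so the check sets what the saving needs against what is collected, and then works out the direction of bias.

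**1. What the saving needs.** For each positive relative: (a) whether the condition was already known, by gene test or clinically, and since when; (b) whether lipid-lowering treatment was already in use.

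**2. What the plan collects.**

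| Source | Known before? | Treated? |
|---|---|---|
| Outside gene report (III.c) | Yes, if tested earlier and the report is submitted | No |
| Outside lipid panel, previous year (III.c), with the lipid date in Appendix A | Shows earlier testing, not diagnosis | No |
| Open CVD risk-factor line (Appendix A) and the elevated-cholesterol topic named in III.a | Possibly, as free text without a date | Not prompted |
| Lipid values (Appendix A) | No | No; there is no on/off-treatment flag |

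A relative diagnosed on lipid levels and treated without a gene test takes the swab, tests positive and looks newly identified. The lipid values do not settle the matter, because a moderate value may reflect treatment. No follow-up contact or review of adult records is described.

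**3. Direction of bias.** Let N be newly identified, untreated carriers and T already-treated carriers who are counted. Let s be the saving assigned to each of the N, and w·s the saving assigned to each of the T. Known but untreated carriers are left aside. If the T gain nothing from the test (assumed):

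counted saving / attributable saving = (N·s + T·w·s) / (N·s) = 1 + w·q/(1 − q), where q = T/(N + T).

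This is above 1 whenever w and q are above 0, so the bias is upward.

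**4. Illustration only.** Neither q nor w is in the documents.

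| q (assumed) | q/(1 − q) | w = 1 | w = 0.5 |
|---|---|---|---|
| 10% | 0.111 | 1.11 | 1.06 |
| 30% | 0.429 | 1.43 | 1.21 |
| 50% | 1.000 | 2.00 | 1.50 |

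The w = 1 column is 1/(1 − q) and requires equal saving per carrier. The w = 0.5 column can also be read as half of the treated carriers being recognised and excluded.

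**5. Scale of the counts.** Section III.b says "It is estimated that 10-20% (approximately 10-20 children) who enroll in the IRB 20-6010 study will be positive for familial hyperlipidemia", and section II describes relatives as untested "despite having a 50% risk of having the same variant". With 4 first-degree relatives tested per child (assumed), carriers number 10 × 4 × 0.5 = 20 to 20 × 4 × 0.5 = 40. One misclassified carrier is then 1/40 = 2.5% to 1/20 = 5% of the count. Wider family uptake would raise the counts; the protocol's ceiling is 5,000 relatives.

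**6. Percent positive.** This depends on the gene result among those tested. Prior diagnosis or treatment does not enter it.

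**The case against.** The strongest objection is that no error has been shown. Section F gives no estimator, comparator, time horizon or unit cost, and never says that every positive relative will be counted. Its wording refers to families, so even the unit is open. A reader might infer that the planned saving is overstated 1.1- to 2.0-fold. The documents do not support that: it requires a count-everyone rule that the plan does not state, an assumed q, equal saving per carrier, and zero gain for those counted in error. Equal saving is doubtful, because section I ties benefit to early identification and already-known carriers may be mostly older. Zero gain is doubtful for relatives who are diagnosed but untreated, since "All participants will be offered access to clinical care for their lipid abnormalities". All of this stands, and it limits the point to direction.

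A second objection is that Appendix A is a bare listing. It has no separate lines for blood pressure or health habits, although III.a promises both, so the REDCap form may be fuller. That is possible, but III.a cites Appendix A as the questionnaire, and nothing in the text names a treatment or prior-diagnosis field.

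A third is that the missing cost method is the larger gap. It is, and it is a separate one. A method can be written after enrolment, whereas status not asked at the visit may be lost.

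**Conclusion.** The point holds as a data-collection gap. With Appendix A as printed, the registry cannot reliably separate carriers it newly identified from those already known or treated, because the three partial routes miss relatives diagnosed or treated on lipid levels alone. If already-treated carriers are counted, the saving is biased upward. That direction rests on their gaining little or nothing from the test. The size cannot be derived from the documents, and the multiples above should not be quoted as estimates. Nor do the documents show that the sponsor intends to count every positive relative; they leave the group undefined. The percent positive is unaffected. The change is worth making because it is cheap and the plan describes no later opportunity to collect the information.

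**What to change.** **Appendix A and the REDCap form.** Add two items:
- Current lipid-lowering medication: yes/no, with start date.
- Diagnosis of familial hyperlipidemia or high cholesterol, or a genetic result, before enrolment: yes/no, with date.

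**Section F.** Define newly identified as having no such diagnosis or genetic result before enrolment, and report that number beside the percent positive. Report the saving separately for three groups: newly identified and untreated, known but untreated, and already treated. Attribute early-identification savings to the first group only. Showing all three lets readers who expect some gain in the second group see it without mixing it into the main figure.

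**Cost.** Two yes/no answers and two dates at the existing visit, and a few sentences in Section F. The form needs an amendment, and anyone already enrolled will have missing values unless contacted again. Prior diagnosis and treatment will rest largely on self-report. The headline saving is likely to be smaller.

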Appendix A. Health Questionnaire

1. Your Name _____
2. Relationship to identified family member (ex. *Mother, father, grandfather, aunt, brother, niece, etc.*) _____
(Check box to indicate which side of the family.) Paternal _____ Maternal _____
3. Age _____
4. Gender _____
5. Ethnicity _____
6. BMI (Weight/Height) _____
7. Lipid results - date _____
 Cholesterol _____
 HDL _____
 LDL _____
 Triglycerides _____
7. CVD Risk factors _____
8. CV disease _____
9. Other Associated Family Members _____
 - a. _____
 - b. _____
 - c. _____
 - d. _____

